5.7 Data Collection and Statistical Considerations

5.7.1 Power Calculations for primary hypotheses

The primary objective of this trial is to assess the efficacy and cognitive adverse effects of RUL-UB ECT and MST in patients with severe depression in a randomized, multi-centre, non-inferiority clinical trial. We will use a combined primary effectiveness endpoint: (1) MST will result in remission rates on the 24-item Hamilton Rating Scale for Depression (HRSD-24) that is non-inferior to that of RUL-UB ECT; **AND** (2) MST will have a superior cognitive adverse effect and tolerability profile compared to RUL-UB ECT assessed with the AMT. However, our sample size calculation will be based on non-inferiority trial calculations that are sufficiently large enough to minimize Type II error[103] and are consistent with previous large, multi-centre ECT trials[9]. RUL-UB ECT can achieve remission in about 50% of patients with a treatment resistant form of depression[10]. Non-inferiority trials such as this proposed study specify a tolerance threshold, with a tolerance of 15% denoting equivalence between the two treatments when the effectiveness of MST can be concluded to be not less than 35%. The total sample size is derived as a function of tolerance and power with a significance level of 0.05. Using these methods, a total sample size of 260 participants (130 per group) will yield 80% power to confirm a non-inferior difference in HRSD-24 remission rates of 15% between the two study groups. This sample size would also provide >95% power to detect a minimally important difference $\geq 25\%$ (absolute risk difference) change on the AMT total score. The primary analysis will proceed once a minimum of 260 participants achieve a clinically determined adequate trial of treatment. We will define a completer as any participant who has received an adequate trial of RUL-UB-ECT or MST as per the definition used in the literature by Sackeim and colleagues [10] (i.e., 8 treatments or meet remission criteria). The overall rate of dropout in a similar past trial at CAMH was less than 3 percent in those receiving fewer than 8 treatments. As such, the sample size of 260 completers will be attainable. Testing of the cognitive outcome will only proceed if non-inferiority is established on remission. This closed testing procedure will ensure the Type I error probability for these two outcomes does not exceed 0.05.

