The hypothesis to be tested is $H_0: \pi_{ECT} - \pi_{MST} \geq 0.15$ versus $H_1: \pi_{ECT} - \pi_{MST} < 0.15$ where π_{ECT} and π_{MST} are the probabilities of remission in the ECT and MST groups respectively. The primary comparison will be a one-sided Z-test in difference of proportions, compared against the non-inferiority margin of 15%. The 15% non-inferiority margin was chosen as a remission rate of 35% remains clinically meaningful in this difficult to treat sample and still higher than more conventional, less invasive treatments for treatment resistant depression (e.g., rTMS at about 20 percent remission [106] and 14 percent with antidepressants [107]). The absolute risk difference (difference in proportions) will be calculated along with 90% and 95% confidence intervals, using standard normal approximations. Since intention to treat (ITT) analysis introduces a conservatism that is undesirable for non-inferiority trials both ITT (i.e. all randomized participants) and completer analyses (i.e. 8 treatments or met remission criteria) will be performed. The primary analysis for Stage 1 will be a completer analysis and a sensitivity analysis will be done secondarily. Inverse probability weighted methods will be employed in an attempt to attenuate the bias resulting from the improper sub-group that a PP results in. We plan to collect the primary outcome data from all patients regardless of treatment compliance to minimize missing data in the outcomes. If outcomes are missing in more than 5% of the patients in the ITT analysis, inverse probability weighting and multiple imputation approaches will be employed to assess and mitigate the effect of missing data. Multiple Imputation by Chained Equations (MICE) will be used to perform the imputations and the following variables will be used in the missing data model: number of failed antidepressant trials, duration of most recent depressive episode, number of major depressive episodes, benzodiazepine use, age, and presence of the other psychiatric comorbidities, e.g. anxiety, duration of illness, not taking psychiatric medication at baseline, treatment duration, and minority racial status. The number of replications for multiple imputations will be based on the proportion of data that is missing, e.g. 10% missing implies 10 replications. For the inverse probability weighting, weights will be estimated from a logistic regression model (with binary dependent variable: dropout vs not dropout) predicting probability of dropout. In order to have a correctly specified model, most of the baseline variables collected will be included (e.g. demographic and clinical characteristics, HRSD score, SSI score, CGI score, ATHF, BSI score, presence of medical and/or psychiatric comorbidities, etc.). It is only necessary for non-inferiority to be established in the unadjusted analysis described to proceed to the stage 2 analysis although additional secondary analyses of this outcome will be performed.

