
An adjusted analysis will be performed using generalized linear models for binary data. Study site will be included as well as clinical variables known to be associated with remission (see again Senn et al.[105] and Pocock et. al.[104]). The following variables will be included in the analysis, which have been shown to be related to response/remission in this population: number of failed antidepressant trials, duration of most recent depressive episode, number of major depressive episodes, and benzodiazepine use (in lorazepam equivalents). The purpose of the adjusted analysis is to ensure the non-inferiority finding is consistent between an unadjusted analysis and one in which predictors of outcome are controlled for. This consistency will be examined in two ways. First, the unadjusted odds ratio and 95% confidence interval will be compared with the adjusted for consistency. Second, the fitted logistic regression model will be used to estimate the probability of response for each subject. An adjusted difference in proportions will be estimated by averaging the predicted probabilities within group and taking the difference. A bootstrap will then be used to generate a distribution of this measurement from which the bias corrected percentiles can be obtained to compare with the 15% non-inferiority margin.

Stage 2 Analysis

In terms of cognitive superiority, we will use the autobiographical memory test (AMT). The binary outcome is defined as a worsening of $\geq 25\%$ on the AMT total score. The hypothesis to be tested is $H_0: \pi_{ECT} - \pi_{MST} = 0$ versus $H_1: \pi_{ECT} - \pi_{MST} \neq 0$ where π_{ECT} and π_{MST} are the probabilities of deterioration in the ECT and MST groups respectively. This primary analysis will be ITT. The hypothesis will be tested with a chi-square test. The absolute risk difference and 95% confidence interval will be computed using standard methods. Secondary analyses will follow a similar approach as in stage 1.

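### The first consistency check compares marginal and conditional odds ratios, off the scale of the 15-point margin, so it cannot show whether non-inferiority survives covariate adjustment; the spurious shift itself is small for a passing result

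*Combined protocol and SAP*

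**What the plan says.** Stage 1 (section 5.8.1) is on the risk-difference scale: "The primary comparison will be a one-sided Z-test in difference of proportions, compared against the non-inferiority margin of 15" percentage points. The same section reports that difference with 90% and 95% intervals.

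A secondary adjusted analysis follows. It is a logistic model with site and four clinical variables, chosen because they are known to be related to remission. Its purpose is to "ensure the non-inferiority finding is consistent between an unadjusted analysis and one in which predictors of outcome are controlled for". Consistency is examined in two ways:

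1. "First, the unadjusted odds ratio and 95% confidence interval will be compared with the adjusted for consistency".
2. Fitted probabilities from the logistic model are averaged inside each arm and subtracted, and bias-corrected bootstrap percentiles of that difference are set against the 15-point margin.

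The plan gives no odds-ratio margin and no criterion for calling the two odds ratios consistent, and does not say that they need not agree. Section 5.8.1 also states that only the unadjusted analysis has to succeed before Stage 2 is tested.

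**The concern.** The odds ratio is non-collapsible. When a covariate predicts remission and the arms differ, the odds ratio within covariate levels lies further from 1 than the overall odds ratio, even if the covariate is distributed identically in the two arms. The covariates here are selected for being prognostic, so a gap between the two odds ratios is expected whenever remission rates differ. If MST is somewhat worse, the adjusted odds ratio will tend to look worse still, with no imbalance to explain it.

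The scale is a separate difficulty. The claim is a 15-point risk difference, and no odds ratio, adjusted or not, says whether that claim holds. What is at stake is how the supporting evidence for the primary finding is read.

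**Working it through.** **Inputs from the documents.** ECT remission: "RUL-UB ECT can achieve remission in about 50% of patients with a treatment resistant form of depression" (section 5.7.1). Margin 15 points, so MST at the margin is 35%. Size: "a total sample size of 260 participants (130 per group) will yield 80% power". Alpha 0.05, used one-sided (sections 5.7.1 and 5.8.1).

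**Assumed.** The documents do not give the strength of the covariates. I take one normally distributed prognostic score, identical in both arms, with linear-predictor SD s = 0.5, 0.75 or 1.0 (covariate AUC about 0.63, 0.69 and 0.74).

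**Step 1. The plan's own figure.** Take 50% in both arms and an unpooled variance. SE = √(2 × 0.25/130) = 0.0620. Power = Φ(0.15/0.0620 − 1.645) = Φ(0.774) = 78.0%, close to the stated 80%. One-sided 0.025 would give 67.7%. So one-sided 0.05 with equal true rates is the reading that comes near the plan.

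**Step 2. Which results pass?** With ECT observed at 50%, a deficit d passes if 0.15 − d > 1.645 × √[(0.25 + (0.5 − d)(0.5 + d))/130]. Equality is at d = 0.048: SE = 0.0619, and 0.150 − 1.645 × 0.0619 = 0.048. MST is then 45.2% and the unadjusted odds ratio is 0.4518/0.5482 = 0.824.

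**Step 3. Adjusted odds ratio under perfect balance.** For each arm g, solve ∫ expit(a_g + s·z) φ(z) dz = p_g. The conditional odds ratio is exp(a_MST − a_ECT). With ECT at 50%, a_ECT = 0. The last row of the table is the margin, where non-inferiority would not be found.

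| ECT v MST | Unadjusted OR | Adjusted OR, s = 0.5 / 0.75 / 1.0 | Largest shift |
|---|---|---|---|
| 50% v 50% | 1.000 | 1.000 / 1.000 / 1.000 | none |
| 50% v 45.2% (just passes) | 0.824 | 0.815 / 0.804 / 0.791 | 4% |
| 50% v 40% | 0.667 | 0.651 / 0.634 / 0.613 | 8% |
| 50% v 35% | 0.538 | 0.520 / 0.499 / 0.474 | 12% |

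The true risk difference in each row is the same with or without the covariate.

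**Step 4. Shift against sampling error.** At the passing limit, SE(log OR) = √[1/(130 × 0.25) + 1/(130 × 0.4518 × 0.5482)] = 0.249. For s = 0.5, 0.75 and 1.0, a_MST is −0.205, −0.218 and −0.234, against ln 0.824 = −0.194. The shifts are 0.05, 0.10 and 0.16 SE. The unadjusted 95% interval is 0.824 × exp(±1.96 × 0.249), about 0.51 to 1.34. At 50% v 35% with s = 1.0 the shift is 0.50 SE.

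**Step 5. Scale.** A 15-point deficit is not one odds ratio. For ECT remission of 40%, 50%, 60% and 70% it is (0.25/0.75)/(0.40/0.60) = 0.500, then 0.538, 0.545 and 0.524 by the same formula. A reader therefore has no fixed odds-ratio value against which to judge the adjusted estimate.

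**Step 6. Does the second check cover the gap?** In a maximum-likelihood logistic model with an intercept and an arm term, the score equations force Σ(y − p̂) = 0 within each arm. The mean fitted probability in each arm is therefore the observed remission proportion, and the difference of these means is the raw difference in the participants fitted. In simulated trials of 130 per arm the two differed by less than 10⁻¹⁵. Predicting every participant under both arms gives a genuinely adjusted estimate; in one simulated data set it was 0.1153 against an unadjusted 0.1154.

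**The case against.** The case for leaving the plan alone is fair in several respects.

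- *No decision depends on the check.* This stands. The adjusted analysis is secondary, Stage 2 is gated on the unadjusted result alone, and no rule attaches to an inconsistent finding.
- *The shift is trivial where it matters.* This largely stands. The check is there to support a non-inferiority finding, so passing results are the relevant ones, and there the shift is at most 0.16 SE. It vanishes if remission rates are equal, which is the assumption under which the stated power roughly reproduces.
- *Reporting both odds ratios is ordinary practice.* This stands as description. The difficulty is the stated use, as evidence that a risk-difference claim survives adjustment.
- *The second check is already on the margin's scale.* That is true of its intent. As worded it reproduces the unadjusted point estimate (Step 6), so it does not supply the missing evidence.

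Two stronger readings are tempting. A reader might infer that the check will often raise a false alarm. In simulation at 50% v 40%, the two 95% intervals disagreed on excluding 1 in 12% of trials with s = 1.0, and in 20% with s = 1.5. But the plan does not use exclusion of 1 as its criterion, those rates include ordinary sampling variation and chance imbalance, and trials with those true rates meet the margin only about 20% of the time. A reader might also infer that a real change in the risk difference would be hidden just as readily. No calculation supports that.

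**Conclusion.** The point holds as one of method, with little numerical consequence. The first check compares quantities that differ by construction when remission rates differ, on a scale that carries no margin, so it cannot do what section 5.8.1 asks of it. For a result that just passes, the built-in shift is 1 to 4% of the odds ratio (0.05 to 0.16 SE). It is zero with equal arms, and reaches 12% (0.50 SE) only at 50% v 35%, where there is no non-inferiority finding to check. These sizes rest on ECT remission of 50%, 130 per arm, exact balance and an assumed covariate SD of 0.5 to 1.0; stronger covariates would enlarge them.

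The documents do not support reading this as a threat to the primary test, its Type I error or entry to Stage 2. What remains is that the adjusted analysis, as written, has no working check on the margin's scale. That makes a change desirable rather than essential.

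**What to change.** Replace the odds-ratio comparison with one on the margin's scale:

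- Show the unadjusted risk difference and the covariate-standardised risk difference side by side, each with a 90% interval against 15 points. The 90% interval matches the one-sided 5% test and is already planned for the unadjusted difference.
- For the standardised difference, use the planned logistic model to predict every participant in the analysis set under both arms, average each set of predictions, and subtract. Do this for the completer set, which is primary in Stage 1, and then for ITT. This also replaces the within-arm averaging of the second check.
- Take the interval for the standardised difference from the bootstrap already planned, refitting the model in each resample.
- Report the adjusted odds ratio as descriptive only, and note that it need not equal the unadjusted one even with perfect balance.

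The model and the data are unchanged. The cost is a few sentences of plan text and slightly more analysis work.

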5.8.2 Secondary Outcome Analysis

Our secondary effectiveness endpoint outlines that MST will have a non-inferior remission rate on the SSI compared to RUL-UB-ECT in patients with depression. Our sample size calculation of 260 subjects was based on non-inferiority trial calculations that are sufficient to minimize Type II error[103] and are consistent with prior NIMH sponsored ECT trials[27]. RUL-UB-ECT and MST can achieve remission in approximately 60% of TRD patients [28, 92].

5.8.3 Adverse Event Analysis

The analysis of all adverse events will include incidence tables by severity, relationship to treatment and baseline parameters. Adverse event rates will be compared between the study groups:

- a. Compare average number of items endorsed on the Columbia ECT Side Effects Schedule between groups after treatment. We anticipate that there will be no significant differences in side effects between these two treatments and will conduct comparisons of safety endpoints at trial conclusion.
- b. Compare AE's between groups
 1. Absolute count of AE experienced during treatment course in both groups
 2. Mean headache score for treatment course
 3. Mean nausea score

4. Mean dizziness
 5. Mean pain
 6. Mean number of treatments with presence of post-ictal confusion or agitation
 7. Mean other AE's
 8. Absolute count of dropout between groups
 9. Absolute count of SAE's between groups
- c. Time to reorientation: 1) Compare the average number of participants between ECT and MST who achieved reorientation within a certain time frame across the first three treatments. 2) Compare the proportion of patients who achieve reorientation between the ECT and MST conditions at treatment sessions one, two, and three.

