3.0 OBJECTIVES AND HYPOTHESES

Primary objective: To assess the efficacy and cognitive adverse effects of MST compared to RUL-UB ECT in patients with depression.

Primary hypothesis/combined effectiveness endpoint: (1) MST will result in remission rates on the 24-item Hamilton Rating Scale for Depression (HRSD-24) that is non-inferior to that of RUL-UB ECT; **AND** (2) MST will have a superior cognitive adverse effect and tolerability profile compared to RUL-UB ECT as assessed with the Autobiographical Memory Test (AMT).

Secondary objective: To assess the efficacy MST compared to RUL-UB ECT in ameliorating suicidal ideation in patients with depression.

Secondary hypothesis/effectiveness endpoint: MST will have a non-inferior remission rate on the SSI compared to RUL-UB-ECT in patients with depression.

Tertiary objective: To refine and develop candidate neurophysiological biomarker, cortical inhibition (CI), using combined transcranial magnetic stimulation and electroencephalography (TMS-EEG) that may predict response to treatment using remission of suicidal ideation as a meaningful clinical indicator.

Tertiary hypothesis/effectiveness endpoint: (1) Change in CI in the DLPFC following MST will significantly predict SSI reduction; (2) Following MST and ECT, increased complexity in course time scales derived through multi-scale entropy will be associated with change in the AMT scores in patients with depression.

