5.1.5 Clinical and Cognitive Measures

Screening and Baseline evaluation:

Prior to screening, potential participants will be seen for a consultation by an ECT/MST attending psychiatrist. Capacity to consent to treatment and research procedures will be assessed and documented. Participants will be screened with the MINI V 6.0 and HRSD-24 to determine eligibility. The MINI V 6.0 assesses current and lifetime depression and other psychiatric disorders. It will be used to clarify psychiatric inclusion and exclusion criteria. Furthermore, a score of greater than or equal to 21 on the HRSD-24 will be used to establish eligibility. The Transcranial Magnetic Stimulation Adult Safety Screen will be used to assess for potential MST risk factors[75]. The Antidepressant Treatment History Form (ATHF) will be used to quantify level of treatment resistance[77, 78]. Demographic information, medical history and concomitant medications information will also be collected at the screening visit. The Clinical Global Impression Scale-Severity (CGI-S)[46] and Young Mania Rating scale (YMRS) will also be completed at baseline. The schedule of assessments is depicted in Table 1 (Appendix A).

Clinical Assessments During and After Treatment:

Clinical outcome measures will be completed at baseline, after every three treatments (or every four treatments to facilitate treatment scheduling) immediately prior to the next treatment session, within four days of the last treatment session, and then six months post-treatment. This latter time point will be part of an exploratory analysis to study the long-term clinical and cognitive outcomes post- ECT or post-MST treatment. The HRSD-24 [74] will be the primary outcome measure. Secondary outcome measures will include the Scale for Suicidal Ideation (SSI)[69], Brief Symptom Inventory (BSI)[79], Clinical Global Impression Severity/Improvement Scale (CGI-S, CGI-I)[80], Quality of Life Enjoyment and Satisfaction Questionnaire (Q-LES-Q)[81], and the Columbia ECT Subjective Side Effects Schedule[82].

Cognitive Assessments

The cognitive battery was designed to comprehensively examine cognitive dimensions that are affected by seizure therapies while minimizing burden on participants[23]. Assessments included in the cognitive battery measure global cognitive function, intellectual abilities, attention, processing speed, verbal fluency, anterograde and retrograde memory, and executive functions. Specific cognitive measures include:

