- (1) Test of Premorbid Function (TOPF)[83] - measures premorbid IQ - baseline only
- (2) Montreal Cognitive Assessment (MoCA)[70, 84] - measures global cognitive function – baseline, end of treatment, follow-up
- (3) three tests from the Delis Kaplan Executive Function System (D-KEFS)[85]: Verbal Fluency, Color-Word Interference, and Tower Test—measures executive functions including verbal fluency, inhibition, cognitive flexibility, and planning—baseline, end of treatment, follow-up
- (4) California Verbal Learning Test- Third Edition (CVLT-3)[86] - measures verbal learning and memory, and effort – baseline, end of treatment, follow-up
- (5) Autobiographical Memory Test (AMT)[87] - measures autobiographical memory recall and specificity – baseline, end of treatment, follow-up
- (6) NIH Toolbox: Flanker Test, Picture Sequence Test, List Sorting Working Memory Test [88]—measures processing speed, attention, visuospatial memory, and working memory—baseline, end of treatment, follow-up
- (7) Time to Reorientation (as used in the PRIDE Study) [89, 90] - measures reorientation time – after the first three treatments

These assessments will be completed upon participant termination of treatment, including both completion of the treatment course or withdrawal from treatment prior to completion.

The specific cognitive measures included in this battery were selected based on the need for 1) measures of global cognitive function and estimated intellectual ability in statistical models, 2) psychometrically sound cognitive measures, 3) cognitive measures with normative data and alternate forms to minimize confounding demographic and practice effects, and 4) maximizing cognitive measurement while minimizing participant burden.

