Appendix A

Table 1. Schedule of Events

Clinical and Cognitive Assessments*	Can be done remotely Y/N	Screening	Baseline		Acute Phase (Weeks 1 – 7*)	Post Acute Phase	6 Month Follow-up
			V1	V2	After every 3 (or 4) treatments		
MINI	Y	X					
Demographics Form	Y	X					
Medical History Form	Y	X					
TASS	Y	X					
HRSD-24	Y	X			X	X	X
ATHF	Y		X				
SSI	Y		X		X	X	X
BSI	Y		X		X	X	X
CGI	Y		X (CGI-S)			X (CGI-I)	X
Q-LES-Q	Y		X			X	X
YMRS	Y		X		X	X	
Columbia ECT Side effects Schedule	Y		X		X	X	X
Concomitant Meds	Y	X	X		X	X	X
Time to Reorientation	N				X (After Tx 1 -3)		
TOPF	Y			X			
MoCA	Y			X		X	X
DKEFS Verbal	Y			X		X	X
DKEFS Color Word Interference	Y			X		X	X
DKEFS Tower Test	N			X		X	X
CVLT-3	Y			X		X	X
AMT	Y			X		X	X
NIH Toolbox: Flanker Test	N			X		X	X
NIH Toolbox: Picture Sequence Test	N			X		X	X

NIH Toolbox: Sorting Working Memory	N			X		X	X
TMS/EEG	N			X		X	
Lab Work** (bloodwork, urine screen)	N	X					
ECG**	N	X					

*This timeline is based on a participant who attends treatment three times per week. However, it is possible that it may take longer to complete the acute phase if treatment is received two times per week at any point throughout the treatment course.

**These procedures will be ordered and completed as per standard clinical practice. The results will be available for screening purposes and will be reviewed by the study doctor and anesthesiologist prior to treatment start.

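### The Columbia side-effect comparison states no baseline term or interval, and the primary hypothesis claims better tolerability on a memory test alone

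*Combined protocol and SAP*

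**What the plan says.** **Columbia analysis.** Section 5.8.3 item a plans to "Compare average number of items endorsed on the Columbia ECT Side Effects Schedule between groups after treatment". It names no time point beyond this, no baseline term, no model and no interval. It adds an expectation: "We anticipate that there will be no significant differences in side effects between these two treatments".

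**Columbia data.** Section 5.1.5 lists the scale among the secondary outcome measures. In Appendix A, Table 1, the row "Columbia ECT Side effects Schedule" is marked at baseline, in the acute phase after every 3 or 4 treatments, post-acute and at 6 months. Section 5.8.2 (secondary outcomes) deals only with remission on the Scale for Suicidal Ideation, so item a is the only analysis described for the Columbia.

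**Other side-effect analyses.** The same section states: "The analysis of all adverse events will include incidence tables by severity, relationship to treatment and baseline parameters". Item b adds nine comparisons. The first is "Absolute count of AE experienced during treatment course in both groups"; the others cover headache, nausea, dizziness, pain, post-ictal confusion or agitation, other adverse events, dropout and serious adverse events. Item c covers reorientation over the first three treatments.

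**Primary claim.** The second half of the combined primary hypothesis in Section 3.0, repeated in Section 5.7.1, reads "MST will have a superior cognitive adverse effect and tolerability profile compared to RUL-UB ECT as assessed with the Autobiographical Memory Test (AMT"). Section 5.1.5 says that this test "measures autobiographical memory recall and specificity".

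**The concern.** There are two separate matters.

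First, a baseline rating of the same scale is usually among the best predictors of the later rating. If it is collected but left out of the comparison, the interval for the arm difference is wider than it needs to be. Because the plan expects no difference, readers will want to know which differences the data rule out. An interval answers that; a bare non-significant result does not.

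Second, the primary hypothesis names two things, cognitive adverse effects and tolerability, and tests only the first. As worded, a positive Stage 2 would let the trial report superior tolerability as a primary finding, while the section that analyses side effects expects none. At stake is the scope of the headline conclusion, not the validity of the test behind it.

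**Working it through.** **1. The plan's own figure.** The only power statement attached to the second primary claim is in Section 5.7.1: more than 95% power on the AMT for a 25-point absolute risk difference with 130 per group. For a two-sided 0.05 test of two proportions, power = Φ[(0.25 − 1.96·SE₀)/SE₁], where SE₀ uses the pooled proportion and SE₁ the separate ones. With the higher rate varied from 26% to 99%, the lowest power is at 62% versus 37%:

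- SE₀ = √(2 × 0.495 × 0.505/130) = 0.0620
- SE₁ = √((0.62 × 0.38 + 0.37 × 0.63)/130) = 0.0600
- power = Φ[(0.25 − 0.1215)/0.0600] = Φ(2.14) = 98.4%

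The statement holds, but for a memory outcome. No power or precision figure is given for the Columbia.

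**2. Precision of the Columbia comparison.** Inputs from the plan: 130 per arm (Section 5.7.1) and a baseline rating (Table 1). Assumptions: both ratings are available for all 130 per arm, the SD is equal in the two arms, and the baseline-to-post correlation ρ is 0.3, 0.5 or 0.7. The documents give neither the SD nor ρ, so results are in SD units.

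- Residual variance after adjustment = 1 − ρ²
- Standard error of the difference = √(1 − ρ²) × √(2/130) = √(1 − ρ²) × 0.1240
- 95% CI half-width = 1.96 × standard error
- Smallest difference detectable with 80% power = (1.96 + 0.842) × standard error

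| | Variance removed | 95% CI half-width (SD) | Detectable difference (SD) | Power for an assumed 0.3 SD |
|---|---|---|---|---|
| Unadjusted | 0% | 0.243 | 0.347 | 67.7% |
| ρ = 0.3 | 9% | 0.232 | 0.331 | 71.8% |
| ρ = 0.5 | 25% | 0.211 | 0.301 | 79.8% |
| ρ = 0.7 | 49% | 0.174 | 0.248 | 92.3% |

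Without adjustment, a true difference of 0.3 SD gives a non-significant result 32% of the time (1 − 0.677), and one of 0.2 SD 64% of the time. A non-significant result would therefore say little by itself, which is the reason to report an interval.

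**3. On-treatment ratings.** A full 21-session course yields six ratings (after sessions 3, 6, 9, 12, 15 and 18) or five (after 4, 8, 12, 16 and 20). Under Section 5.1.1, treatment ends once remission is confirmed, no minimum number of sessions applies, and MST may need more sessions. The number of ratings therefore depends on outcome and possibly on arm. This limits their use as the main comparison.

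**4. The tolerability wording, place by place.**

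- Section 1.4.1, aim 1: lists tolerability and cognitive adverse effects as separate items.
- Section 3.0, primary objective: names efficacy and cognitive adverse effects only.
- Sections 3.0 and 5.7.1, primary hypothesis: adds tolerability, measured by the AMT.
- Section 5.1.4: distinguishes the raters who assess efficacy and tolerability from the neuropsychological technicians.
- Section 5.8.1, Stage 2: tests cognition only, as worsening of at least 25% on the AMT.
- Section 5.8.3: analyses side effects and expects no significant difference.

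The word appears in the hypothesis but in neither the objective nor the test.

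**The case against.** **Side effects are not reduced to one number.** From item a alone, a reader might infer that the trial compares side effects only as a single post-treatment count and ignores those that arise and resolve during treatment. The documents do not support this. Items b and c compare adverse event counts, headache, nausea, dizziness, pain, confusion and reorientation, several of them over the treatment course. This stands, and it confines the first matter to the Columbia.

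**No bias.** A reader might also infer that counting complaints present before treatment distorts the comparison. Randomization balances them in expectation, so the arm difference is unbiased. This stands too; the loss is precision only.

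**Adjustment is not ruled out.** Item a neither states nor excludes a baseline term. That is fair, and the point is one of specification. Section 5.8.1 does set out covariates for remission, so the silence here is worth closing.

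**No equivalence claim is made.** The line anticipating no significant differences is an expectation. Nowhere do the documents say that a non-significant result will be read as equal tolerability, so that inference should not be drawn.

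**The tolerability wording is editorial.** Stage 2 is confined to cognition, and the hypothesis says openly that the AMT is the measure. Memory impairment is also one of the anticipated adverse events in Section 5.2.6, so the AMT bears on part of tolerability. It is one entry in a long list, however. Changing the wording alters no test, but it does alter what a positive test may be said to show.

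**Conclusion.** Both matters hold, with limited scope.

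For the Columbia, the plan leaves out a free gain in precision on a listed secondary outcome. The gain is 9% to 49% of the variance for ρ between 0.3 and 0.7, which shortens the 95% CI half-width from 0.243 SD to between 0.232 and 0.174 SD. The range rests on an assumed correlation and on 130 participants per arm with both ratings. The comparison is not biased, and side effects as a whole are analysed more widely than item a.

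For the primary hypothesis, the tolerability claim goes beyond its measure and sits poorly with the expectation in Section 5.8.3. This conclusion needs no assumption.

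Neither matter affects the sample size of 260, the test at either stage or the Type I error.

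**What to change.** **Section 5.8.3 item a.** State that the post-acute Columbia item count will be compared between arms with the baseline count as covariate, and that the adjusted difference will be reported with a 95% CI. On-treatment ratings may be summarised by arm as supportive information only, because their number depends on when remission ends treatment. A repeated-measures model over all visits would first need a defined estimand for that.

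**Sections 3.0 and 5.7.1.** Strike the reference to tolerability from the second part of the primary hypothesis, so that the claim is limited to autobiographical memory as measured by the AMT. Report tolerability from Section 5.8.3.

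**Cost.** Wording only: no new data, visits or participants, and no change to the Stage 1 or Stage 2 tests. The one downside is a slightly narrower primary claim.
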